10.5.2 Other secondary efficacy objectives

10.5.2.1 Assess the overall response rate at Week 12, Week 36, and Week 48

Proportion of overall responders (enrolled patients with mUFC \leq ULN or have at least 50% reduction in mUFC from baseline and $>$ ULN) at Week 12, Week 36 and Week 48 will be summarized using point estimates and Clopper-Pearson 95% CIs by treatment arms and for overall patients. For the osilodrostat arm, denominator will be the number of patient randomized to osilodrostat; whereas for placebo arm, denominator will be number of randomized patients switched to osilodrostat.

10.5.2.2 Assess the change in mUFC during the Core and optional Extension periods of the study

For the actual and percentage change in mUFC from baseline, descriptive summaries will be provided for every visit in Core and optional extension phase at which UFC is collected. 95% CIs for the percentage change from baseline will also be provided by treatment arms and for overall patients.

10.5.2.3 Compare the time-to-first control of mUFC during the placebo-controlled period between patients randomized to osilodrostat and placebo

Time-to-first control of mUFC during the placebo control period will be analyzed using Kaplan-Meier plots and the logrank test. Time-to-first control of mUFC is defined as the time (in days) from randomization to the time of the first post-baseline mUFC collection that was \leq ULN (based on central lab result) before discontinuation or completion of placebo-controlled period, whichever is earlier.

10.5.2.4 Assess the time-to-escape during treatment of osilodrostat up to Week 48

For patients who attained normal mUFC (\leq ULN), time-to-escape will be analyzed using Kaplan-Meier plots. This will be performed by randomized treatment assignment and for the overall trial population. Time-to-escape is defined as the time (in weeks) from the first collection of post-baseline normal mUFC (\leq ULN) to the first mUFC $>$ 1.3 x ULN on 2 consecutive visits on the highest tolerated dose of osilodrostat and not related to a dose interruption or dose reduction due to safety reasons. Time-to-escape will not be assessed for patients during the first 26 weeks.

Patients that have dose interruption or dose reduction for safety reasons will be censored at the time of the first dose interruption.

10.5.2.5 Assess the change from baseline in cardiovascular and metabolic related parameters associated with Cushing's disease during the core period of the study

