2.6.2 Statistical hypothesis, model, and method of analysis

For the key secondary endpoint, the statistical null hypothesis states that the proportion of complete response rate at Week 36 is $< 30\%$. The analysis of the key secondary objective will be based on the 2-sided 95% exact confidence interval (CI) constructed using the Clopper-Pearson method in FAS patients receiving osilodrostat treatment. Patients with missing mUFC at Week 36 will be counted as non-responders. If the lower bound of this 95% confidence interval is $\geq 30\%$, the null hypothesis will be rejected and the complete response rate will be considered at least 30% at Week 36. Patients randomized to placebo who do not switch to osilodrostat will not be included in this analysis.

The above testing on the key secondary objective will only be carried out if the null hypothesis for the primary objective is rejected. This sequential procedure will ensure preservation of the overall 2-sided type 1 error at 5%.

As supportive analysis of the key secondary objective, analysis will be repeated using PPS patients receiving osilodrostat treatment. In addition, the same analysis will be performed in the patients randomized to osilodrostat arm only. For each supportive analysis, the 2-sided 95% exact confidence interval of the complete response rate at Week 36 will be provided.

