2.6.3 Handling of missing values/censoring/discontinuations

Placebo patients who discontinued during Period 1 and not received osilodrostat treatment in this study will not be included in the analysis. Patients who received osilodrostat treatment with missing mUFC at Week 36 will be considered as non-responders for key secondary analysis. In order to evaluate the impact of missing mUFC, multiple imputations assuming missing at random will be considered as sensitivity analyses.

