2.7 Analysis of secondary efficacy objectives

2.7.1 Assess the overall response rate at Week 12, Week 36, and Week 48

Proportion of complete responders (enrolled patients with $mUFC \leq ULN$), partial responders (enrolled patients with $mUFC > ULN$ and at least 50% reduction from baseline), and overall responders (enrolled patients with $mUFC \leq ULN$ or have at least 50% reduction in mUFC from baseline and $> ULN$) will be summarized using point estimates for every scheduled visit in the core and extension phase at which UFC is collected by treatment arm. Response rate will also be provided for all patients in the open-label period. 95% 2-sided CIs will be provided at Week 12, Week 36 and Week 48. To calculate the response rate during the open label treatment period, for the osilodrostat arm, the denominator will be the number of patients randomized to osilodrostat in Period 1; whereas for the placebo arm, the denominator will be the number of patients randomized to placebo in Period 1 who switched to osilodrostat. The FAS will be used for this analysis.

2.7.2 Assess the change in mUFC during the Core and Extension periods of the study

- Change in mUFC from baseline during the placebo-control period only

2.7.3 For the actual value and change in mUFC from baseline during placebo-control period, descriptive summaries will be provided. Compare the time-to-first control of mUFC during the placebo-controlled period between patients randomized to osilodrostat and placebo

Time-to-first control of mUFC is defined as the time (in days) from first study treatment date to the time of the first post-baseline mUFC collection that was $\leq ULN$ (based on central lab result) before discontinuation or completion of placebo-controlled period, whichever is earlier. It will be defined as censored at the last mUFC collection date if the mUFC was not controlled during the placebo-controlled period.

Time-to-first control of mUFC during the placebo control period will be analyzed using Kaplan-Meier plots and the logrank test. The quantiles of time-to-first control and corresponding two-sided 95% CI will be calculated using Kaplan-Meier methodology. FAS will be used for this analysis.

2.7.4 Assess the time-to-escape during treatment of osilodrostat up to Week 48

Escape is defined as the first loss of control of UFC that meets all of the following criteria:

- prior normalization of UFC has occurred ($mUFC \leq ULN$)

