2.1.1 General definitions

Study drug

Throughout the SAP, investigational drug refers to osilodrostat, and study treatment/ study drug refers to osilodrostat or placebo.

Overall study period

The overall study period refers to the complete study duration (including core and extension period) with data presented by the osilodrostat arm, placebo arm excluding placebo-control period, and overall patients (excluding data of placebo arm collected during placebo-control period).

Date of study treatment

The start date of study treatment is defined as the first date when a nonzero dose of study treatment was administered and recorded on DAR eCRF. The date of first administration of study treatment in period 1 will be referred as the start date of study treatment.

The last date of study treatment is defined as the last date when a nonzero dose of study drug was administered and recorded on DAR eCRF.

Study day

Study day is used to represent an evaluation, a measurement or an event (e.g. AE onset, laboratory abnormality occurrence, disease progression, etc.). The study day is calculated as

Study day = date of assessment – start date of study treatment + 1 (if date of assessment is after start date of study treatment)

Study day = date of assessment – start date of study treatment (if date of assessment is before start date of study treatment)

For any assessment or events such as baseline characteristics or medical history that is supposed to occur prior to start date of the study treatment, study day will be negative. There is no Day 0 defined.

Study day associated with a UFC assessment

The study day associated with a UFC assessment at any particular visit is defined as the study day of the last UFC sample collection for that visit.

Calculating mean UFC

It is scheduled to collect three individual 24 hours Urine Free Cortisol (UFC) samples at visits Week 1, 12, 36, and 48, and two UFC samples at all other visits. For a given visit, Mean Urine Free Cortisol (mUFC) is the mean of all available (with a minimum of 2) individual UFC values determined at a central laboratory. In the case that only one or no UFC value is available, the mUFC will be considered missing for that visit.

Calculation of proportions of responders

All randomized patients will be included in the analysis for calculating the proportion of responders at time points up to Week 48 based on the FAS.

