2.2.1 Full Analysis Set

The Full Analysis Set (FAS) comprises all randomized patients who have received at least one dose of study drug (osilodrostat or placebo). According to the intent-to-treat (ITT) principle, patients will be analyzed according to the treatment and stratum they have been assigned to during the randomization. This is the default analysis set for efficacy. The randomization is stratified by history of pituitary irradiation yes/no.

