2.7 Analysis of secondary efficacy objectives

2.7.1 Assess the overall response rate

Proportion of complete responders (enrolled patients with $mUFC \leq ULN$), partial responders (enrolled patients with $mUFC > ULN$ and at least 50% reduction from baseline), and overall responders (enrolled patients with $mUFC \leq ULN$ or have at least 50% reduction in $mUFC$ from baseline and $> ULN$) will be summarized using point estimates for all scheduled visits in the core and extension phase at which UFC is collected (provided [adequate follow-up](#), as defined in section 2.1.1, [Criteria of adequate follow-up for time points in the extension phase](#)).

Due to the COVID-19 (Coronavirus) pandemic, planned visits may have been cancelled, potentially resulting in missing UFC evaluations. Patients with insufficient information due to any reason at a visit will be considered as non-responder for that visit. The number of patients with non-response due to missing visits linked to the pandemic (recorded as COVID-19 related PD) will be summarized.

To explore the impact of the COVID19 pandemic in the extension phase, individual patient's doses and overall response status over time will be graphically displayed together with pandemic start date.

The FAS will be used for this analysis.

2.7.2 Assess the change in mUFC during the Core and Extension periods of the study

For the actual value and change in $mUFC$ from baseline, descriptive summaries will be provided for every scheduled visit in the core and extension (provided [adequate follow-up](#), as defined in section 2.1.1, [Criteria of adequate follow-up for time points in the extension phase](#)) at which UFC is collected. The FAS will be used for the analysis.

2.7.3 Compare the time-to-first control of mUFC during the placebo-controlled period between patients randomized to osilodrostat and placebo

The results were reported in the interim CSR, and will not be repeated for the final CSR.

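### Final SAP responder denominators: placebo patients who never switched count as failures at Weeks 14 to 48, and extension rule 3 has no written Amendment 02 limit

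*SAP*

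**What the plan says.** **Up to Week 48.** Final SAP 2.1.1 (calculation of proportions of responders) states, on the FAS: "All randomized patients will be included in the analysis for calculating the proportion of responders at time points up to Week 48". Its FAS (2.2.1) takes in anyone randomized who took a single dose, placebo included. A patient who is in the denominator but stopped before the time point is a non-responder (2.1.1). Section 2.7.1 adds: "Patients with insufficient information due to any reason at a visit will be considered as non-responder for that visit". The core visits are reported again, because response "will be summarized using point estimates for all scheduled visits in the core and extension phase at which UFC is collected".

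**The documents it builds on.** Protocol 10.5.2.1, for overall response: "whereas for placebo arm, denominator will be number of randomized patients switched to osilodrostat". Core SAP 2.7.1, for the open-label period: "for the placebo arm, the denominator will be the number of patients randomized to placebo in Period 1 who switched to osilodrostat". The key secondary analysis at Week 36 takes the same line in core SAP 2.6.2, "Patients randomized to placebo who do not switch to osilodrostat will not be included in this analysis", and in 2.6.3, "Placebo patients who discontinued during Period 1 and not received osilodrostat treatment in this study will not be included in the analysis".

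**Extension.** Final SAP 2.1.1 gives three rules. Rule 1 drops patients who declined the extension. Rule 2 keeps completers until their own end-of-treatment extension visit under Amendment 02. Rule 3 keeps discontinuers for the visits they could have made up to Week 96 or data cut-off, whichever is earlier. Section 1.1.4 says that after Amendment 02 extension patients had to leave within 4 weeks of approval at their site, or by Week 96 if sooner. A time point is reported if at least 15 patients are available for it.

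**The concern.** A placebo patient who leaves in Period 1 never takes osilodrostat. Counting that patient as a failure at the open-label visits mixes non-exposure with non-response. It also departs from the protocol and the core SAP without a word in Section 4 of the final SAP, where changes to protocol-specified analyses are meant to be listed. The two clinical study reports could then print different placebo-arm and overall rates for the same patients, visits and data.

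In the extension, rules 2 and 3 treat patients at one site differently. A completer leaves the denominator at site exit. A discontinuer can stay in it as a failure at a later visit that nobody at that site could attend. Rule 3 is also not limited to patients who received osilodrostat, so on its wording non-switchers stay in there too. Both features can only lower the reported rate.

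**Working it through.** **1. The plan's own figure.** The one stated figure that depends on the open-label denominator is the probability above 98% that the Clopper-Pearson lower bound exceeds 30% at Week 36, given a 60% true rate (protocol 10.9; final SAP Section 3). The smallest count with a lower bound of at least 30% is 29 of 69, and P(X ≥ 29 | 69, 0.60) = 99.9%. With 11 placebo patients excluded, the most that the plan's assumption of under 50% discontinuation allows among 23, n = 69 − 11 = 58, the count is 25 and the probability 99.7%. The stated figure is reproduced and not in dispute.

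**2. One patient traced through the rules.** Take a placebo patient who stops study drug at Week 8.
- FAS: yes, because dosed.
- Scheduled follow-up: to Week 12, plus a visit 30 days after last dose (protocol Table 7-1a and 7.1.6). No Week 14 to 48 UFC collection is scheduled.
- Core SAP 2.7.1, open-label visits: not in the denominator.
- Key secondary analysis, Week 36: not in the denominator.
- Final SAP 2.1.1 with 2.7.1, Weeks 14 to 48: in the denominator, non-responder.

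**3. Size at Weeks 14 to 48.** Inputs: planned split 46 osilodrostat and 23 placebo (final SAP 1.1), and an assumed 60% response among exposed patients (the plan's Week 36 value). Let k be the number of dosed placebo patients who never switched; the documents do not give it. The switched-only rate is 60% in both groups. Under the final SAP the placebo arm shows 60% × (23 − k)/23 and the overall group 60% × (69 − k)/69.

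| k | Placebo arm | Overall |
|---|---|---|
| 0 | 60.0% | 60.0% |
| 1 | 60 × 22/23 = 57.4% | 60 × 68/69 = 59.1% |
| 2 | 60 × 21/23 = 54.8% | 60 × 67/69 = 58.3% |

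k = 2 is roughly the plan's 10% drop-out allowance applied to 23 patients. The osilodrostat arm's rates at these visits do not move.

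**4. Rule 3.** The SAP's example has a last visit at Week 84 and 20 weeks to data cut-off, giving min(96, 84 + 20) = Week 96. Only the two written limits enter; no site approval date is used.

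Who could be affected is limited by the calendar:
- The 18 patients treated by 20-Nov-2017 (Amendment 1 rationale) reach Week 96 (first dose + 672 days) by 23-Sep-2019, before Amendment 2 was issued on 20-Dec-2019.
- The Amendment 2 rationale places local approval after the last core completion, expected by the end of February 2020. Taking 29-Feb-2020 as the earliest approval, exit is due by 28-Mar-2020. Subtracting 672 days gives 26-May-2018, so only first doses after that date could be cut short of Week 96.
- This window is an upper bound. Overcounting also needs a UFC visit (Week 60, 72, 84 or 96) to fall between site exit and data cut-off, and neither date is given.

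Per affected discontinuer at the 15-patient reporting floor, assuming 60% among the other 14: 60 × 14/15 = 56.0%.

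**The case against.** **The final SAP may already exclude non-switchers.** Its overall study period (2.1.1) leaves out the placebo arm's placebo-controlled period, Section 4 ends by carrying an approach forward to the final report, and the introduction refers to the core SAP for the core analyses. None of this repairs the denominator. The overall study period removes data, not patients. The closing sentence of Section 4 follows the safety text, so its reach to efficacy is at best unclear. Section 2.7.1 reports the core visits again under the final SAP's own rule.

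**There may be nothing to correct.** The final SAP postdates the core database lock, so the sponsor could know how many placebo patients switched. If all did, the two denominators agree. That stands. It is also fair that an all-FAS denominator is an explicit, conservative choice in keeping with intent to treat; if it was intended, it belongs in Section 4.

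**Rule 3 may be meant to stop at site exit.** A visit after mandatory exit is arguably not one a patient could have made. This stands as an ambiguity. But only rule 2 cites Amendment 02, and a programmer following the rule 3 example would apply no such limit.

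**Stronger readings that the documents do not support:**
- A reader might take the under-50% discontinuation figure as a forecast of up to 11 non-switchers. It is a tolerance in a probability calculation and says nothing about how many failed to switch.
- A reader might treat the 45 patients on treatment in December 2019 as the extension denominator. Ten of them were still in the core phase.
- A reader might infer that the trial's main conclusions are at risk. Final SAP 2.5 and 2.6 do not repeat the primary and key secondary analyses.
- Counting osilodrostat-exposed discontinuers as non-responders is a stated conservative rule and is not faulted here.

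**Conclusion.** Minor, but wrong as written for Weeks 14 to 48: the final SAP's rule conflicts with protocol 10.5.2.1 and core SAP 2.7.1, and Section 4 does not declare it. The size depends on an unreported number of non-switchers and may be zero. Under the planned split and the assumed 60%, each non-switcher costs about 2.6 points in the placebo arm (60/23) and 0.9 points overall (60/69).

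Rule 3 is an omission on its literal wording and an ambiguity on a generous one. Its effect may also be zero, and is 4 points per affected discontinuer at the 15-patient floor under the same 60% assumption. All affected outputs are descriptive. The primary and key secondary tests and the osilodrostat arm's core-phase rates are unaffected.

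**What to change.** 1. Up to Week 12, keep all FAS patients by randomized arm. From Week 14 on, including the extension and the overall rate, include only placebo-arm patients who switched to osilodrostat. Otherwise, list the all-FAS denominator in Section 4 as a change. Protocol 10.5.2.1 names switched patients without setting Week 12 apart, so the Week 12 denominator should be recorded there too.
2. Give rule 3 a third limit: the end of participation under Amendment 02 at the patient's site, at the latest 4 weeks after site approval. Apply it consistently with rule 2, because completers may leave at their own end-of-treatment visit before the 4 weeks are up.
3. State that the 15-patient threshold applies to this corrected denominator, since availability for the analysis is not defined.

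The cost is SAP wording, site approval dates that the sponsor should hold, and a small programming change.

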2.2.4 Optional Extension Phase

At the end of the Core study (Week 48) patients receiving clinical benefit from osilodrostat have the option to enter a 48-week optional Extension phase (Weeks 48 to 96). Additional safety and efficacy data will be collected during this period. Patients currently enrolled in the optional extension phase must end study participation within 4 weeks after Protocol Amendment 02 is approved at the site, or by Week 96, whichever occurs first. Refer to [Section 4.1](#) for more details.

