1.1.4 Optional Extension phase

At Week 48, patients had the option to enter an open-label Extension phase. Patients who did not enter the optional extension discontinued osilodrostat at Week 48 and concluded with a Post-Treatment (End of Study) visit after 30 days off study drug. Prior to Protocol Amendment 02, the optional extension ended at Week 96 for all patients, and patients still deriving benefit from osilodrostat treatment had the option to continue treatment on study until other treatment options became available. After Protocol Amendment 02, patients enrolled in the optional extension phase had to end study participation within 4 weeks after Protocol Amendment 02 was approved at their site, or by Week 96, whichever occurred first. Patients who are benefitting from study treatment, have the option to enter a separate long-term safety follow-up study or stop study treatment. Patients who do not enter the long-term safety follow-up study will discontinue osilodrostat and conclude the study with a Post-Treatment (End of Study) visit after 30 days off study drug.

During the extension phase the dose of osilodrostat is maintained at the established effective dose unless a change is required based on mUFC results collected at Weeks 48, 60, 72, and 84.

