For calculation of proportion of responders beyond Week 48 (e.g. a time point in extension phase), the following rules will be applied to determine whether patients are included in the analysis.

- 1) patients who declined to enter optional extension phase after completion of the core phase will be excluded.
- 2) patients who completed the extension phase will be included until their individual end of study dates (EOT EXT visit, as per Protocol Amendment 02)
- 3) patients who discontinued prior to the data cutoff date for the Final DBL will be included for visits they could have completed if they had continued until week 96 or data cut off for the analysis (whatever occurs earlier), but excluded for further visits. For example, if the last completed scheduled visit for an early discontinued patient is Week 84, and the time between data cutoff and last completed scheduled visit is 20 weeks, he/she will be included in the analyses up to Week 96.

If included in the analysis for calculating the proportion of responders at a given timepoint, patients who discontinued before this timepoint will be counted as non-responders.

Criteria of adequate follow-up for time points in the extension phase

For a given time point in the extension phase, it will be considered to have adequate follow-up to be included in the reporting activities if there are at least 15 patients available for the analysis at that time point.

Time unit

A year length is defined as 365.25 days. A month length is 30.4375 days (365.25/12). If duration is reported in months, duration in days will be divided by 30.4375. If duration is reported in years, duration in days will be divided by 365.25.

Baseline

Baseline values for efficacy and safety evaluations are defined as the last assessment available before or on the start date of study treatment. If patients have no assessments as defined above, the baseline result will be missing.

Follow up

Regular safety follow-up is scheduled at 30 days after the last date of study treatment. In addition, for patients who discontinued study treatment during Period 1 (Weeks 1 to 12), reasonable efforts should be made to follow the patients and perform the assessments as indicated in protocol visit evaluation schedule table (protocol Table 7-1a) up to and including Week 12.

Visit number and time window

The following visit schedule tables are generated from TDM/TV domain.

Table 2-1 Scheduled visits in core phase

Core study Visit	Day/Week	Clarifying Notes

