2.3.2 Patient disposition

Patient disposition will be tabulated for FAS. The summary will include the number of patients who were randomized, treated, permanently discontinued from study treatment.

The following summaries will be presented: % is based on total number of FAS patients:

- Number (%) of patients who were randomized (based on data from IRT system)
- Number (%) of patients who were randomized but not treated (based on eCRF DAR page not completed for any study treatment component)
 - Primary reason for not being treated (based on eCRF End of Treatment Phase Completion page)
- Number (%) of patients who were treated (based on eCRF DAR page of each study treatment completed with non-zero dose administered)
 - Number (%) of patients who discontinued the study treatment phase (based on eCRF End of Treatment Phase page)
 - Primary reason for study treatment phase discontinuation (based on eCRF End of Treatment Phase Completion page)
 - Number (%) of patients who discontinued in Period 1 (prior to Week 12)
 - Primary reason for discontinuation in Period 1
 - Number (%) of patients who discontinued in Period 2 (Weeks 13 to 48)
 - Primary reason for discontinuation in Period 2
- Number (%) of patients who completed core phase (week 48)
 - Completed Week 48 and did not enter Extension phase
 - Completed Week 48 and entered Extension phase
 - Number (%) of patients who discontinued in the Extension
 - Primary reason for discontinuation in the Extension
 - Discontinued at or prior to Week 72 but after Week 48
 - Discontinued prior to Week 96 but after Week 72
 - Discontinued after Week 96
 - Number (%) of patients who completed extension

* Patients who completed Week 48 and did not enter extension phase are not counted as discontinuations.

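### After Week 48 the final SAP drops core completers who declined the extension but keeps earlier discontinuers as non-responders, and no planned analysis keeps the non-entrants

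*SAP*

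**What the plan says.** Up to Week 48, final SAP 2.1.1 puts all randomized patients in the denominator, based on the FAS. After Week 48 three rules apply:

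- **Rule 1:** "patients who declined to enter optional extension phase after completion of the core phase will be excluded".
- **Rule 2:** "patients who completed the extension phase will be included until their individual end of study dates".
- **Rule 3:** patients who discontinued before the cut-off "will be included for visits they could have completed if they had continued until week 96 or data cut off for the analysis", whichever is earlier. The rule is not restricted to patients who entered the extension.

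For anyone retained, "patients who discontinued before this timepoint will be counted as non-responders".

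Final SAP 2.7.1 then summarizes response at all core and extension visits as one series, on the FAS. It treats insufficient information for any reason as non-response.

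Three other places bear on who the non-entrants are:

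- Protocol 2.2.4 says that "patients receiving clinical benefit from osilodrostat have the option to enter a 48-week optional Extension phase". Core SAP 2.1 (01-Apr-2019) carries the same condition. Final SAP 1.1.4 does not: "At Week 48, patients had the option to enter an open-label Extension phase".
- Final SAP 1.1.4 also says "Patients who did not enter the optional extension discontinued osilodrostat at Week 48".
- The footnote to the disposition summary in final SAP 2.3.2 says "Patients who completed Week 48 and did not enter extension phase are not counted as discontinuations".

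**The concern.** Two patients with nearly the same course are treated in opposite ways. One stops at Week 44 and is carried as a failure to Week 96 or cut-off. The other completes Week 48 above the ULN, declines the extension, and leaves both numerator and denominator. If entry is linked to benefit, the patients removed may differ in response from those kept.

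Reporting long-term efficacy is a stated purpose of the final SAP. A reader who follows the rates from Week 12 through the extension would take them to describe one population, and could read part of a selection effect as durability of response. Nothing planned would show how large that part is.

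**Working it through.** **1. The plan's own figure.** The only number attached to these rules is the worked example for rule 3: last completed visit Week 84, cut-off 20 weeks later, included up to Week 96. Check: min(84 + 20, 96) = 96. This agrees.

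**2. The asymmetry at, say, Week 72.**
- Stops at Week 44: rule 3 applies, contribution 0/1.
- Completes Week 48 above the ULN and declines: rule 1 applies, contribution 0/0. Under the 2.3.2 footnote this patient is not a discontinuation, so rule 3 does not naturally bring the patient back.

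**3. Effect of rule 1 at a fixed visit.** Let R be responders among those kept, N the denominator with non-entrants kept as non-responders, and d the number of non-entrants. Rule 1 gives R/(N-d); keeping non-entrants as non-responders gives R/N. The ratio is N/(N-d), above 1 whenever d > 0.

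Inputs: N = 69 is the planned sample size. R = 41 is an assumption, from the 60% planning rate for Week 36 (0.60 × 69 = 41.4). The values of d are assumptions.

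| d | Kept as non-responders | Rule 1 | Difference (points) |
|---|---|---|---|
| 2 | 41/69 = 59.4% | 41/67 = 61.2% | +1.8 |
| 5 | 59.4% | 41/64 = 64.1% | +4.6 |
| 7 | 59.4% | 41/62 = 66.1% | +6.7 |
| 10 | 59.4% | 41/59 = 69.5% | +10.1 |

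**4. If non-entrants are credited with their own response.** Assume 7 core discontinuers (about the 10% planning drop-out), d = 7, and 75% response in the other 55 (41.25). Rule 1 gives 41.25/62 = 66.5%. Keeping non-entrants with response rate r gives (41.25 + 7r)/69:
- r = 0: 59.8%
- r = 25%: 62.3%
- r = 50%: 64.9%
- r = 66.5%: 66.5% (break-even)
- r = 100%: 69.9%

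Rule 1 therefore raises the rate only when non-entrants respond less often than the patients retained.

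**5. Rules 2 and 3 over time.** Same scenario, with a share of the 55 entrants gone because they reached their end-of-extension visit, while the 7 discontinuers stay as non-responders:

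| Share ended | Rule 1 | Non-entrants as non-responders |
|---|---|---|
| 0% | 66.5% | 59.8% |
| 25% | 30.94/48.25 = 64.1% | 30.94/55.25 = 56.0% |
| 50% | 20.63/34.5 = 59.8% | 20.63/41.5 = 49.7% |
| 75% | 10.31/20.75 = 49.7% | 10.31/27.75 = 37.2% |

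The rule 1 rate falls over time, but at each visit it stays above the alternative.

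**6. Comparison with the core SAP.** Core SAP 2.7.1 planned response rates at every core and extension visit. For the open-label period it set denominators as patients randomized to osilodrostat and placebo patients who switched. It removes no non-entrants. Section 4 of the final SAP lists no denominator change.

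**The case against.** The strongest reply is that rule 1 is openly prespecified and that limiting an optional-extension summary to patients who were followed is common. The rates are descriptive. The response objective itself covers Weeks 12, 36 and 48 only, and non-entrants who were not responding already count as such at Week 48. The disposition table will also show how many completers did not enter. All of this stands, and it limits the weight of the point. It does not supply a rate that keeps the non-entrants or show their Week 48 response.

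Two stronger readings are tempting, and the documents do not support them:

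- *That rule 1 removes patients without benefit.* The rule speaks of patients who declined. If the offer went only to those benefiting, as protocol 2.2.4 says, a patient without benefit had nothing to decline and no rule names that patient. Final SAP 1.1.4 and the 2.3.2 footnote also pull in different directions on whether non-entrants discontinued, so two programmers could derive different denominators.
- *That the long-term response curve rises through selection.* The rise is certain only at a given visit, and only against counting non-entrants as non-responders. With their own response credited, the sign can reverse (step 4), and rules 2 and 3 lower later rates (step 5).

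The final SAP postdates the reporting of the core results. That strengthens the case for a sensitivity analysis but says nothing about why the rule was chosen.

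**Conclusion.** The point holds in limited form. The denominator changes at Week 48 within one visit series: core completers who declined leave, earlier discontinuers stay as failures, and no planned analysis keeps the non-entrants. Since protocol 2.2.4 ties entry to benefit, the post-Week 48 rates are conditional on a selection that is plausibly, though not demonstrably, related to outcome.

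Against the non-responder convention that the SAP applies elsewhere, rule 1 raises the rate at a visit by the factor N/(N-d). The illustrative gain is 1.8 points (d = 2) to 10.1 points (d = 10). It rests on an assumed 41/69 and assumed d, because the documents give neither the number of non-entrants nor their Week 48 response. The true size is therefore unknown, and so is the direction relative to non-entrants' own response. The primary (Week 12) and key secondary (Week 36) results are untouched.

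**What to change.** 1. In final SAP 2.1.1, state how every Week 48 completer who does not enter is handled, whether the patient declined or was not offered entry, and reconcile section 1.1.4 with the 2.3.2 footnote.
2. In 2.7.1, add a sensitivity analysis of each post-Week 48 visit that keeps all non-entrants as non-responders.
3. Beside the main rates, report the number of non-entrants and their Week 48 response, and label those rates as excluding core completers who did not enter.
4. In section 4, list the change of denominator from core SAP 2.7.1.

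A finer rule that keeps or drops non-entrants by Week 48 response or by reason for leaving is not advised. It would make the denominator depend on outcome, and the disposition summary lists no reasons for non-entry.

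The cost is SAP wording and one extra table from data already collected. The sensitivity figure will be less favourable than the main rate and is deliberately conservative, so it should be presented as such.
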